10.2.1 Modification of diet in renal disease (MDRD) equation

Estimated Glomerular filtration rate (mL/mins/1.73 m²) = 175 × (Scr)^{-1.154} × (Age)^{-0.203} × (0.742 if Female) × (1.212 if African-American).

10.3 APPENDIX 3: AES AND SAES: DEFINITIONS AND PROCEDURES FOR RECORDING, EVALUATING, FOLLOW-UP, AND REPORTING

10.3.1 Definition of AE

AE definition

- An AE is any untoward medical occurrence in a participant or clinical study participant, temporally associated with the use of study intervention, whether or not considered related to the study intervention.
- NOTE: An AE can therefore be any unfavorable and unintended sign (including an abnormal laboratory finding), symptom, or disease (new or exacerbated) temporally associated with the use of study intervention.

Definition of unsolicited and solicited AE

- An unsolicited AE is an AE that was not solicited using a participant diary and that is communicated by a participant who has signed the informed consent. Unsolicited AEs include serious and non-serious AEs.
- Potential unsolicited AEs may be medically attended (ie, symptoms or illnesses requiring a hospitalization, or emergency room visit, or visit to/by a health care provider). The participants will be instructed to contact the site as soon as possible to report medically attended event(s), as well as any events that, though not medically attended, are of participant concern. Detailed information about reported unsolicited AEs will be collected by qualified site personnel and documented in the participant's records.
- Unsolicited AEs that are not medically attended nor perceived as a concern by participant will be collected during interview with the participants and by review of available medical records at the next visit.
- Solicited AEs are predefined local at the injection site and systemic events for which the participant is specifically questioned, and which are noted by the participants in their diary.

Events meeting the AE definition

- Any abnormal laboratory test results (hematology, clinical chemistry, or urinalysis) or other safety assessments (eg, ECG, radiological scans, vital signs measurements), including those that worsen from baseline, considered clinically significant in the medical and scientific judgment of the Investigator (ie, not related to progression of underlying disease), or more severe than expected for the participant's condition), eg:

- Leading to IMP discontinuation or modification of dosing, and/or,
- Fulfilling a seriousness criterion, and/or,
- Defined as an AESI.
- Exacerbation of a chronic or intermittent pre-existing condition including either an increase in frequency and/or intensity of the condition.
- New conditions detected or diagnosed after study intervention administration even though it may have been present before the start of the study.
- Signs, symptoms, or the clinical sequelae of a suspected drug-drug interaction.
- Signs, symptoms, or the clinical sequelae of a suspected overdose of either study intervention or a concomitant medication.
- Signs, symptoms, or the clinical sequelae of any medication errors and misuse with the IMP.
- "Lack of efficacy" or "failure of expected pharmacological action" per se will not be reported as an AE or SAE. Such instances will be captured in the efficacy assessments. However, the signs, symptoms, and/or clinical sequelae resulting from lack of efficacy will be reported as AE or SAE if they fulfill the definition of an AE or SAE.

Events NOT meeting the AE definition

- Any clinically significant abnormal laboratory findings or other abnormal safety assessments which are associated with the underlying disease, unless judged by the Investigator to be more severe than expected for the participant's condition.
- The disease/disorder being studied or expected progression, signs, or symptoms of the disease/disorder being studied, unless more severe than expected for the participant's condition.
- Medical or surgical procedure (eg, endoscopy, appendectomy): the condition that leads to the procedure is the AE.
- Situations in which an untoward medical occurrence did not occur (social and/or convenience admission to a hospital).
- Anticipated day-to-day fluctuations of pre-existing disease(s) or condition(s) present or detected at the start of the study that do not worsen.

10.3.2 Definition of SAE

An SAE is defined as any adverse event that, at any dose:

- a) Results in death.**
- b) Is life-threatening.**

The term "life-threatening" in the definition of "serious" refers to an event in which the participant was at risk of death at the time of the event. It does not refer to an event, which hypothetically might have caused death, if it were more severe.

c) Requires inpatient hospitalization or prolongation of existing hospitalization.

- In general, hospitalization signifies that the participant has been admitted (usually involving at least an overnight stay) at the hospital or emergency ward for observation and/or treatment that would not have been appropriate in the physician's office or outpatient setting. Complications that occur during hospitalization are AEs. If a complication prolongs hospitalization or fulfills any other serious criteria, the event is serious. When in doubt as to whether "hospitalization" occurred or was necessary, the AE should be considered serious.
- Hospitalization for elective treatment of a pre-existing condition that did not worsen from baseline is not considered an AE.

d) Results in persistent or significant disability/incapacity

- The term disability means a substantial disruption of a person's ability to conduct normal life functions.
- This definition is not intended to include experiences of relatively minor medical significance such as uncomplicated headache, nausea, vomiting, diarrhea, influenza, and accidental trauma (eg, sprained ankle) which may interfere with or prevent everyday life functions but do not constitute a substantial disruption.

e) Is a congenital anomaly/birth defect.

f) Other situations:

- Medical or scientific judgment should be exercised by the Investigator in deciding whether SAE reporting is appropriate in other situations such as important medical events that may not be immediately life-threatening or result in death or hospitalization but may jeopardize the participant or may require medical or surgical intervention to prevent one of the other outcomes listed in the above definition. These events should usually be considered serious.

Note: The following list of medically important events is intended to serve as a guideline for determining which condition has to be considered as a medically important event. The list is not intended to be exhaustive:

- Intensive treatment in an emergency room or at home for:
 - Allergic bronchospasm.
 - Blood dyscrasias (ie, agranulocytosis, aplastic anemia, bone marrow aplasia, myelodysplasia, pancytopenia, etc).
 - Convulsions (seizures, epilepsy, epileptic fit, absence, etc).
- Development of drug dependence or drug abuse.
- ALT $>3 \times$ ULN + total bilirubin $>2 \times$ ULN or asymptomatic ALT increase $>10 \times$ ULN.
- Suicide attempt or any event suggestive of suicidality.
- Syncope, loss of consciousness (except if documented as a consequence of blood sampling).
- Bullous cutaneous eruptions.

10.3.3 Recording and follow-up of AE and/or SAE

AE and SAE recording

- When an AE/SAE occurs, it is the responsibility of the Investigator to review all documentation (eg, hospital progress notes, laboratory reports, and diagnostics reports) related to the event.
- The Investigator will then record all relevant AE/SAE information.
- It is **not** acceptable for the Investigator to send photocopies of the participant's medical records to the Sponsor's representative in lieu of completion of the required form.
- There may be instances when copies of medical records for certain cases are requested by the Sponsor's representative. In this case, all participant identifiers, with the exception of the participant number, will be redacted on the copies of the medical records before submission to the Sponsor's representative.
- The Investigator will attempt to establish a diagnosis of the event based on signs, symptoms, and/or other clinical information. Whenever possible, the diagnosis (not the individual signs/symptoms) will be documented as the AE/SAE.

Assessment of intensity

The Investigator will make an assessment of intensity for each AE and SAE reported during the study and assign it to 1 of the following categories:

- Mild: An event that is easily tolerated by the participant, causing minimal discomfort and not interfering with everyday activities.
- Moderate: An event that causes sufficient discomfort to interfere with normal everyday activities.
- Severe: An event that prevents normal everyday activities. An AE that is assessed as severe should not be confused with an SAE. "Severe" is a category used for rating the intensity of an event; and both AEs and SAEs can be assessed as severe.

An event is defined as "serious" when it meets at least 1 of the predefined outcomes as described in the definition of an SAE, NOT when it is rated as severe.

Assessment of causality

- The Investigator is obligated to assess the relationship between study intervention and each occurrence of each AE/SAE.
- A "reasonable possibility" of a relationship conveys that there are facts, evidence, and/or arguments to suggest a causal relationship, rather than that a relationship cannot be ruled out.
- The Investigator will use clinical judgment to determine the relationship.

- Alternative causes, such as underlying disease(s), concomitant therapy, and other risk factors, as well as the temporal relationship of the event to study intervention administration will be considered and investigated.
- For causality assessment, the Investigator will also consult the IB and/or product information, for marketed products.
- The Investigator must review and provide an assessment of causality for each AE/SAE, and document this in the medical notes.
- There may be situations in which an SAE has occurred, and the Investigator has minimal information to include in the initial report to the Sponsor's representative. However, **it is very important that the Investigator always make an assessment of causality for every event before the initial transmission of the SAE data to the Sponsor's representative.**
- The Investigator may change his/her opinion of causality in light of follow-up information and send an SAE follow-up report with the updated causality assessment.
- The causality assessment is one of the criteria used when determining regulatory reporting requirements.

Follow-up of AEs and SAEs

- The Investigator is obligated to perform or arrange for the conduct of supplemental measurements and/or evaluations as medically indicated or as requested by the Sponsor's representative to elucidate the nature and/or causality of the AE or SAE as fully as possible. This may include additional laboratory tests or investigations, histopathological examinations, or consultation with other health care professionals.
- If a participant dies during participation in the study or during a recognized follow-up period, the Investigator will provide the Sponsor with a copy of any post-mortem findings including histopathology.
- New or updated information will be recorded in the originally submitted documents.
- The Investigator will submit any updated SAE data to the Sponsor within 24 hours of receipt of the information.

10.3.4 Reporting of SAEs

SAE reporting to the Sponsor via an electronic data collection tool

- The primary mechanism for reporting an SAE to the Sponsor's representative will be the electronic data collection tool.
- If the electronic system is unavailable, then the site will use the paper SAE data collection tool (see next section) to report the event within 24 hours.
- The site will enter the SAE data into the electronic system as soon as it becomes available.
- After the study is completed at a given site, the electronic data collection tool will be taken off-line to prevent the entry of new data or changes to existing data.

- If a site receives a report of a new SAE from a study participant or receives updated data on a previously reported SAE after the electronic data collection tool has been taken off-line, then the site can report this information on a paper SAE form (see next section) or to the Sponsor's representative by telephone.
- Contacts for SAE reporting can be found in the investigator site file.

SAE reporting to the Sponsor via paper data collection tool

- Facsimile transmission of the SAE paper data collection tool is the preferred method to transmit this information to the Sponsor's representative.
- In rare circumstances and in the absence of facsimile equipment, notification by telephone is acceptable with a copy of the SAE data collection tool sent by overnight mail or courier service.
- Initial notification via telephone does not replace the need for the Investigator to complete and sign the SAE data collection tool within the designated reporting time frames.
- Contacts for SAE reporting can be found in the investigator site file.

10.4 APPENDIX 4: CONTRACEPTIVE AND BARRIER GUIDANCE

10.4.1 Risk associated with pregnancy

The effects of isatuximab on reproductive toxicity, pregnancy and lactation have not been investigated in formal toxicity studies. Therefore, the effects of isatuximab on reproductive organs in males and females are unknown. However, isatuximab is an IgG antibody, it may cross into the placenta and possibly affect embryonal or fetal growth and development. Therefore, the following contraceptive measures are required for males and females of childbearing potential.

Pomalidomide is structurally related to thalidomide. Pomalidomide was found to be teratogenic in both rats and rabbits when administered during the period of major organogenesis. If pomalidomide is taken during pregnancy, a teratogenic effect of pomalidomide in humans is expected. Therefore, a risk minimization plan to prevent pregnancy must be observed. All study participants must comply with the requirements of Pomalidomide Pregnancy Prevention Plan recommendations (Appendix 15, [Section 10.15](#)) or the country specific risk management plan in countries where pomalidomide is not supplied by the Sponsor.

10.4.2 Contraception guidance

10.4.2.1 Criteria for females of childbearing potential

This protocol defines a FCBP as a sexually mature female who:

- Has achieved menarche at some time point.
- Has not undergone a permanent sterilization method including:
 - Documented hysterectomy.

- Documented bilateral salpingectomy.
- Documented bilateral oophorectomy.
- Has not been naturally postmenopausal (amenorrhea following cancer therapy does not rule out childbearing potential) for at least 24 consecutive months (ie, has had menses at any time in the preceding 24 consecutive months). A high follicle stimulating hormone (FSH) level in the postmenopausal range may be used to confirm a postmenopausal state in women not using hormonal contraception or hormonal replacement therapy (HRT). However, in the absence of 24 months of amenorrhea, a single FSH measurement is insufficient.

If fertility is unclear (eg, amenorrhea in adolescents or athletes) and a menstrual cycle cannot be confirmed before first administration of study intervention, additional evaluation should be considered.

10.4.2.2 Contraception guidance for female subjects

- If locally required, acceptable contraceptive methods are limited to those which inhibit ovulation as the primary mode of action.
- Females of childbearing potential enrolled in this protocol must agree to use two reliable forms of contraception simultaneously or to practice complete abstinence from heterosexual intercourse during the following time periods related to this study:
 - For at least 28 days before starting study treatment,
 - And throughout the entire duration of pomalidomide treatment,
 - And during dose interruptions,
 - And for at least 5 months after study treatment discontinuation.
- The two methods of reliable contraception must include one highly effective method and one additional effective (barrier) method.
- Highly effective contraception with low user dependency is preferred.
- A FCBP must be referred to a qualified provider of contraceptive methods if needed.

CONTRACEPTIVES^a ALLOWED DURING THE STUDY INCLUDE:

Highly effective methods^b that have low user dependency *Failure rate of <1% per year when used consistently and correctly.*

- Implantable progestogen-only hormone contraception associated with inhibition of ovulation.
- Intrauterine device (IUD).
- Intrauterine hormone-releasing system (IUS).
- Bilateral tubal occlusion.
- Azoospermic partner (vasectomized or due to a medical cause).

Azoospermia is a highly effective contraceptive method provided that the partner is the sole sexual partner of the woman of childbearing potential and the absence of sperm has been confirmed. If not, an additional highly effective method of contraception should be used.

Note: documentation of azoospermia for a male participant can come from the site personnel's review of the participant's medical records, medical examination, or medical history interview.

Highly effective methods^b that are user dependent *Failure rate of <1% per year when used consistently and correctly.*

- Combined (estrogen- and progestogen-containing) hormonal contraception^c associated with inhibition of ovulation.
 - Intravaginal.
 - Transdermal.
 - Injectable.
- Progestogen-only hormone contraception associated with inhibition of ovulation.
 - Oral.
 - Injectable.
- Sexual abstinence.

Sexual abstinence is considered a highly effective method only if defined as refraining from heterosexual intercourse during the entire period of risk associated with the study intervention. The reliability of sexual abstinence needs to be evaluated in relation to the duration of the study and the preferred and usual lifestyle of the participant.

- a Contraceptive use by men or women should be consistent with local regulations regarding the use of contraceptive methods for those participating in clinical studies.
- b Failure rate of <1% per year when used consistently and correctly. Typical use failure rates differ from those when used consistently and correctly.
- c A patient can use 'oral' combination if they have discontinued pomalidomide.
As per pomalidomide Summary of Product Characteristics (SmPC), combined oral contraceptive pills are not recommended because of the increased risk of venous thromboembolism in patients with multiple myeloma taking pomalidomide and dexamethasone.

Note: Periodic abstinence (calendar, ovulation, symptothermal, post-ovulation methods), withdrawal (coitus interruptus), spermicides only, and lactational amenorrhea method (LAM) are not acceptable methods of contraception for this study. Male condom and female condom should not be used together (due to risk of failure from friction).

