A FCBP must have a negative serum or urine pregnancy test with a sensitivity of at least 25 mIU/mL within 10 to 14 days prior to and again within 24 hours of starting study treatment and must either commit to continue abstinence from heterosexual intercourse or begin TWO acceptable methods of birth control, one highly effective method and one additional effective method AT THE SAME TIME, at least 28 days before she starts study treatment, during dose interruptions and for at least 5 months following discontinuation of study treatment. An FCBP must also agree to ongoing pregnancy testing during the entire duration of treatment.

Informed Consent

I 08. Capable of giving signed informed consent as described in Appendix 1 ([Section 10.1.3](#)) which includes compliance with the requirements and restrictions listed in the ICF and in this protocol.

Other Inclusion Criteria

I 09. Introduced as per Protocol Amendment 01: Country-specific requirement applicable for Norwegian clinical sites; see Appendix 8, [Section 10.8](#) (Country-specific requirements).

- a) Male participants that agree to not donate semen or sperm during therapy or for at least 4 weeks following discontinuation of pomalidomide or 5 months following discontinuation of isatuximab.**
- b) Participants that agree to not donate blood during therapy and for at least 3 months following discontinuation of pomalidomide.**

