6.2.6 Pomalidomide

Countries, where commercial supplies are desirable based on the country specific regulatory requirements, Pomalidomide from commercial supplies can be used. Otherwise, it will be re-labeled by the Sponsor according to Good Manufacturing Practice guidelines before supplies are provided by the study sites.

When commercial supplies will be used:

- Please refer to package insert or SmPC for further details as regards to formulation, storage, and handling procedures.
- When applicable the Pomalidomide Pregnancy Prevention Plan (Appendix 15, [Section 10.15](#)) or the country specific risk management plan (in countries where pomalidomide is not supplied by the Sponsor) has to be followed to ensure adherence of the pregnancy risk mitigation plan already in place in addition to the protocol requirements.

For a regional or national emergency declared by a governmental agency that results in travel restrictions, confinement, or restricted site access, pomalidomide may be supplied at the site or from the PI/site/Sponsor to the participant via a Sponsor-approved courier company, where allowed by local regulations and agreed upon by the participant during the time the measures are applied.

Further details as regards to formulation, storage and handling procedures will be provided in Package Insert or SmPC of commercial study treatment.

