6.5 DOSE MODIFICATION

Dose modifications are permitted according to the guidelines described in this section.

The participant may have a dose omitted for any IMP within a cycle if toxicity occurs and the participant does not recover within 3 days after the planned day of planned infusion/administration. If a participant experiences several toxicities and there are conflicting recommendations, the most conservative dose adjustment recommended (dose reduction/omission/delay appropriate to the most severe toxicity) should be followed. Within a cycle, the treatment window is ± 1 day for each of QW IMP administrations and ± 3 days for each of Q2W IMP administrations.

Cycle delays are permitted in case of toxicity (see [Section 6.5.7](#)). Cycle is considered delayed if Day 1 is performed more than 3 days after the planned Day 1 of this cycle. Once a dose of IMP has been decreased, intra-participant re-escalation back to the previous dose level is not permitted, except for dexamethasone dose reduction in a context of intercurrent condition neither related to dexamethasone adverse event nor related to multiple myeloma that might require a transient dose reduction. If a dose reduction is required, it is to be applied compared to the last dose level received by the participant.

Administration of the IMP will be discontinued in the event of an AE that persists despite appropriate dose modifications or any other AE that, in the opinion of the Investigator, warrants discontinuation.

All changes to study treatment administration must be recorded in the eCRF. Participants will receive the next cycle of study treatment after recovery of the toxicity as described below. If one of the IMPs is permanently discontinued, the other IMPs can be continued until PD, unacceptable toxicity, or participant's wish to discontinue further study treatment. The end of study treatment in this case will be 30 days after the date of the last study treatment administration.

Recommendations for dose adjustments of IMPs due to AEs are described in [Table 13](#), [Table 14](#), [Table 15](#) (SC arm) and [Table 16](#).

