7.1.1 Permanent discontinuation

Permanent treatment discontinuation is any treatment discontinuation associated with the definitive decision from the Investigator not to re-expose the participant to the study treatment at any time during the study, or from the participant not to be re-exposed to the study treatment whatever the reason. In rare instances, it may be necessary for a participant to permanently discontinue study intervention.

If one of the study treatments is prematurely permanently discontinued, then other drug(s) can be continued until disease progression or unacceptable toxicity or participant's wish to discontinue further study treatment. During this period the participant will remain in the study and continue being assessed per SoA. If all study treatments are permanently discontinued, the visit will be treated as the last dosing day with the IMPs, with subsequent relevant assessments per SoA.

In case of permanent treatment discontinuation due to disease progression, follow up will be every 3 months for further antimyeloma therapy, second primary malignancies, PFS2, and survival until death, or final OS analysis cut-off date, whichever occurs first. See the SoA for data to be collected at the time of discontinuation of study intervention and follow-up and for any further evaluations that need to be completed.

7.1.1.1 *List of criteria for permanent discontinuation*

The participants may withdraw from study treatment if they decide to do so, at any time and irrespective of the reason, or this may be the Investigator's decision. All efforts should be made to document the reason(s) for treatment discontinuation and this should be documented in the eCRF.

Isatuximab, pomalidomide, and/or dexamethasone can be discontinued permanently. The participant will remain on study treatment until the last study treatment is discontinued. The reason for permanent discontinuation will be captured in the appropriate eCRF page.

All efforts should be made to document the reason for discontinuation of treatment with the study treatment:

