9.2.1 General considerations

Myeloma response and progression will be determined by Independent Review Committee based on central laboratory M-protein analysis and central radiology review using IMWG 2016 criteria.

The following stratification factors will be used:

- MM isotype (IgG versus non-IgG).
- Body weight (≤ 65 kg, > 65 to ≤ 85 kg, and > 85 kg).
- Number of prior lines (1-2 versus ≥ 3).

Primary and secondary endpoints will be analyzed by treatment arm.

Study treatment is defined as isatuximab (SC/IV) in combination with pomalidomide and dexamethasone. First dose of study treatment is defined as the first starting dose of any study intervention of isatuximab, pomalidomide or dexamethasone. Last dose of study treatment is defined as the last dose of any study intervention of isatuximab, pomalidomide, or dexamethasone.

For each of the safety parameters, the baseline will be defined as the last value or measurement taken up to the first dose of study treatment.

The observation period will be divided into 3 segments:

- The **pre-treatment** period is defined as the time the ICF is signed until the first dose of the study treatment administration.
- The **treatment-emergent (TE) period** is defined as the period from the first study treatment administration to the last study treatment administration +30 days.
- The **post-treatment period** is defined as the time starting 31 days after the last study treatment is administered to study closure or death, whichever comes first.

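### Two pregnancy-prevention instructions fall short of the protocol's own rules: the Appendix 4 visit check confirms one contraceptive method where two are required, and the counselling forms give 28 days for blood donation where the protocol gives 3 months

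*Protocol*

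**What the plan says.** **Methods required.** Inclusion criterion I 07 b (Section 5.1) requires abstinence or two simultaneous methods, one highly effective and one additional. They apply "at least 28 days before she starts study treatment, during dose interruptions and for at least 5 months following discontinuation of study treatment". Section 10.4.2.2 repeats the two-method rule and specifies that the second method is a barrier.

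**Visit check.** Section 10.4.4.1 has the investigator confirm at each visit that the woman is still using a highly effective form of contraception. It does not mention the second method or abstinence. The matching check in Appendix 15 (plan section 2.5.2.1) asks for two reliable methods or a commitment to complete abstinence.

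**Windows after treatment.** Section 10.4.4.3 bars blood donation for at least 3 months after study treatment. Appendix 15 (plan section 2.5.3 and both counselling forms) gives at least 28 days after the last pomalidomide dose. The forms give the same 28 days for women's contraception and breastfeeding and for men's condom use and sperm donation. The protocol adds 5-month windows for these in Sections 5.1, 10.4.2.2, 10.4.2.3, 10.4.4.1 and 10.4.4.2.

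**On-treatment bullet.** In Section 10.4.2.2 the bullet for the treatment period is "And throughout the entire duration of pomalidomide treatment". The first and last bullets of the same list refer to study treatment as a whole.

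**Isatuximab can outlast pomalidomide.** Section 6.5: "If one of the IMPs is permanently discontinued, the other IMPs can be continued until PD". Section 7.1.1: "The participant will remain on study treatment until the last study treatment is discontinued". Section 9.2.1: "Last dose of study treatment is defined as the last dose of any study intervention of isatuximab, pomalidomide, or dexamethasone".

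**The concern.** These are working safeguards against fetal exposure, in a regimen whose oral drug is expected to be teratogenic (Section 10.4.1). A coordinator who uses the visit check as written confirms half of what I 07 b demands. A counsellor who reads out the form tells every participant, at every dispensing, a blood-donation period shorter than the protocol's. The form carries no pointer to the longer period.

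The bullet naming only pomalidomide raises a related question, because treatment with isatuximab after pomalidomide stops is a planned path. Tables 13 and 14 stop pomalidomide but not isatuximab after a third Grade 4 neutropenia episode, Grade 4 thromboembolism or Grade 4 neuropathy.

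**Working it through.** The plan gives no statistical figure to reproduce here. The check sets the texts side by side and counts days.

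**1. Methods confirmed at a visit**

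| Source | Methods |
|---|---|
| I 07 b; Section 10.4.2.2 (requirement) | two, or complete abstinence |
| Appendix 15, plan section 2.5.2.1 (check) | two, or complete abstinence |
| Section 10.4.4.1 (check) | one |

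The Section 10.4.4.1 check is the only one of the three that stops at one method.

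**2. Windows after treatment**

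| Item | Counselling forms | Protocol |
|---|---|---|
| Blood donation | 28 days after pomalidomide | 3 months after study treatment |
| Women's contraception | 28 days after pomalidomide | 5 months after study treatment |
| Breastfeeding | 28 days after pomalidomide | 28 days after pomalidomide or 5 months after isatuximab, the later |
| Men's contraception | 28 days after pomalidomide | 28 days after pomalidomide or 5 months after isatuximab, the later |
| Sperm donation | 28 days after pomalidomide | 4 weeks after pomalidomide or 5 months after isatuximab (the later, per I 07 a) |

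**3. Size of the differences.** Assume that all study drugs stop on the same day, and take 3 months as 91 days and 5 months as 152 days.

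- Blood donation: 91 − 28 = 63 days. By calendar, 3 months is 89 to 92 days, so the range is 61 to 64.
- The 5-month items: 152 − 28 = 124 days. By calendar, 5 months is 150 to 153 days, so the range is 122 to 125.

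If isatuximab continues for g days after pomalidomide, these become g + 63 and g + 124. The protocol gives no value for g, so no larger figure is claimed.

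**4. Like for like on pomalidomide alone.** For breastfeeding, men's contraception and sperm donation, the protocol's own pomalidomide component is 28 days or 4 weeks, so the difference is 28 − 28 = 0. The 124 days there come entirely from isatuximab's separate 5-month window, which a pomalidomide form does not cover. For women's contraception the protocol states one 5-month window after study treatment and gives no separate pomalidomide period. Blood donation differs even on pomalidomide alone: I 09 b (Norwegian sites) gives 3 months after pomalidomide itself, against 28 days on the forms, again 63 days.

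**5. Does the bullet leave a gap?** Section 10.4.1 cites isatuximab's possible placental passage and concludes "Therefore, the following contraceptive measures are required for males and females of childbearing potential". I 07 b and the last bullet of the list run to 5 months after study treatment, which ends with the last drug given. Section 10.4.3.1 continues pregnancy testing to 5 months after isatuximab. A footnote in Section 10.4.2.2 allows combined oral contraception once pomalidomide has stopped, so it presumes that contraception continues. There is no gap.

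**The case against.** The strongest reply is that nothing binding is missing. The Section 10.4.4.1 check points back to a definition given earlier in Appendix 4, where two methods are mandatory. Appendix 15 forbids dispensing if two methods were not used. All windows are stated as minimums, so the longer one governs. Appendix 15 is another company's versioned, pomalidomide-only plan, and its silence on isatuximab is to be expected. Section 6.2.6 says the plan is followed "to ensure adherence of the pregnancy risk mitigation plan already in place in addition to the protocol requirements". The consent form and the information sheet listed in Appendix 15 are not in the text at hand, so participants may be told the longer periods there.

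Most of this stands, and it rules out three stronger readings that a reader might infer:

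- **That women on isatuximab alone need no contraception.** The adjacent bullets, I 07 b and Sections 10.4.1 and 10.4.3.1 say otherwise.
- **That the 124-day differences are contradictions of the same size as the blood-donation one.** They mostly reflect a pomalidomide document omitting isatuximab's window.
- **That sites using a country plan have a weaker safeguard.** Section 10.4.1 allows such a plan ("or the country specific risk management plan in countries where pomalidomide is not supplied by the Sponsor"), but those plans are not in the protocol and may contain the two-method check.

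The reply does not remove two points. The definition reference in Section 10.4.4.1 concerns what counts as highly effective, and the check still names one method. The blood-donation periods differ even when only pomalidomide is considered. The additive statement in Section 6.2.6 sits under commercial supply, and the forms do not repeat it.

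**Conclusion.** The point holds as a minor inconsistency in operative safety instructions. Two items need correction: the one-method visit check against a two-method requirement, and 28 days against at least 3 months for blood donation. The second is about 63 days (61 to 64) if all study drugs stop together, and it concerns every participant. The forms' silence on the 5-month windows is an omission worth a note: about 124 days on the same-day assumption, nearly all of it attributable to isatuximab. The pomalidomide-only bullet is a tidy-up.

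The stricter rules already bind, so the risk is misreading rather than an absent safeguard. Sample size, power, type I error and all endpoints are unaffected. The protocol does not give the number of women of childbearing potential, so exposure to the visit-check wording cannot be sized.

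**What to change.** 1. **Section 10.4.4.1:** have the investigator confirm one highly effective method plus one additional effective (barrier) method, or complete abstinence.
2. **Head of Section 10.15:** add a study-specific note, to be used with the forms or with any country plan, stating that the longer protocol windows apply:
   - blood donation: at least 3 months after study treatment;
   - women's contraception: at least 5 months after study treatment;
   - breastfeeding, men's contraception and sperm donation: 28 days after pomalidomide or 5 months after isatuximab, whichever is later.

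   Placing this at protocol level avoids editing another company's versioned form. It also reaches men and blood donation at country-plan sites, which the visit check cannot.
3. **Section 10.4.2.2, as a tidy-up:** make the on-treatment bullet refer to study treatment (pomalidomide and/or isatuximab).

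The cost is two wording corrections and one short note in the next amendment, with the IRB/IEC approval that Section 10.1.1 describes. No eligibility criterion, visit, test or data item changes.
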